## 7.4 Data Analysis

- 1) This will involve a mixed methods analysis. We will perform thematic analyses to identify common themes arising from focus group discussions and in-depth interviews. The quantitative questionnaires will be analysed using standard statistical analyses, including Chi

squared tests and logistic regression to analyse relationships between reported knowledge, attitudes and practices, and demographic variables such as gender, age and location.

- 2) For the feasibility and acceptability analysis we will also perform thematic analysis to generate themes of acceptance of the TPHD-LAMP assay amongst healthcare workers, laboratory staff and patients.
- 3) Cost-effectiveness: This analysis will involve using a decision tree model to weigh up the costs attributed to either test. The model will include the sensitivity and specificity of both tests, costs of person time required to perform the test and other variables that will affect if the TPHD-LAMP assay is suitable for routine diagnostics and surveillance.

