#### **1.8 Primary objectives:**

- 1) Perform active case searching and collect household and community level data to identify risk factors associated with yaws transmission and disease.
- 2) Assess the accuracy, acceptability and feasibility of the TPHD-LAMP assay for *T. pallidum* and *H. ducreyi* diagnosis under programmatic conditions in yaws endemic areas in Ghana, Cote d'Ivoire and Cameroon to determine its suitability as a diagnostic in yaws eradication programmes.
- 3) Testing the *Treponema pallidum* macrolide resistance (TPMR)-LAMP assay in a field setting.

- 4) Establish other infectious causes of non-yaws ulcers using specific PCR tests and next generation sequencing techniques, including novel devices such as employing the Minion for nanopore sequencing.
- 5) Collect data on community, patient and healthcare worker knowledge, attitudes and practices in relation to yaws.
- 6) Determine the acceptability and feasibility and cost effectiveness of the TPHD-LAMP assay.

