### 3.2 Study Sites

In each of the three countries, national reporting data will be used to select at least three districts that are highly endemic for yaws, facilitating rapid fulfilment of the sample size required number of yaws cases for the diagnostic accuracy study. The number of villages/communities selected will depend on prevalence of the disease. This exercise will be conducted with the yaws programme national coordinators in the three endemic countries.

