### **7.3 Data collection**

Attitudes and practices in relation to yaws and identifying community needs: In each community, we will invite a sample of key groups including community health workers, opinion leaders and parents and guardians of children to participate in focus group discussions and semi-structured interviews about yaws and related skin diseases. As this is a qualitative evaluation, we have not performed a formal sample size calculation but will aim to achieve data saturation. For the community, members will be selected with an equal portion of males and females and a range of ages to ensure a representative sample. All focus group discussion and interviews will be conducted in English or French with local translators available if another language is preferred. All interviews and focus groups will be recorded, transcribed and translated if necessary. After being transcribed, recordings will be deleted. Common themes identified from the focus group discussions will be used to develop a questionnaire relating to their experiences and perceptions of: the cause of the disease and its transmission; its

diagnosis; healthcare seeking attitudes and factors (barriers/facilitators) influencing this. This questionnaire will be circulated to other communities and key stakeholders enabling us to obtain quantitative data to validate the hypotheses generated from the focus group discussions.

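### Section 7.4 specifies no allowance for clustering by community when questionnaire answers are tested against location; if location means district or country, the named tests exceed their nominal 5%

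*Combined protocol and SAP*

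**What the plan says.** Primary objective 5 (section 1.8) is to "Collect data on community, patient and healthcare worker knowledge, attitudes and practices in relation to yaws". Section 7.3 describes focus groups and interviews whose themes feed a questionnaire: "This questionnaire will be circulated to other communities and key stakeholders enabling us to obtain quantitative data to validate the hypotheses generated" in those discussions. Its statement on sample size, "As this is a qualitative evaluation, we have not performed a formal sample size calculation but will aim to achieve data saturation", concerns the qualitative part. No number of questionnaire respondents appears anywhere.

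On analysis, section 7.4 item 1 introduces an open list of methods: "The quantitative questionnaires will be analysed using standard statistical analyses, including Chi". The rest of that sentence gives the methods and the variables to be related: "squared tests and logistic regression to analyse relationships between reported knowledge, attitudes and practices, and demographic variables such as gender, age and location". It does not say whether location is the community, the district, the country or a type of setting. Neither 7.4 nor any other section mentions a random effect, GEE, a robust variance, a survey method or a design effect.

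On geography, section 3.2 says that in each country "national reporting data will be used to select at least three districts that are highly endemic for yaws", so there are at least nine districts in all. It adds: "The number of villages/communities selected will depend on prevalence of the disease". The number of communities that receive the questionnaire is not given.

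**The concern.** Pearson's chi-squared test and ordinary logistic regression treat respondents as independent. People of one community share health workers, schools, past yaws campaigns and beliefs, so their answers tend to resemble each other. A location variable above community level varies only between communities. Its effective sample size is therefore closer to the number of communities than to the number of respondents. If this is ignored, p-values are too small and confidence intervals too narrow.

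Ordinary village-to-village variation could then be reported as a real difference between districts, countries or settings in yaws knowledge or care seeking. The questionnaire's stated purpose is to validate hypotheses, so such differences could be read as confirmed. These are a separate dataset, set of outcomes and set of tests from the risk-factor regression in section 4.8, so a change there would not reach 7.4.

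**Working it through.** **Figure to reproduce.** None. The plan states no sample size, power or error rate for sub-study 4.

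**Inputs from the plan.** At least 3 districts in each of 3 countries, so at least 9 (section 3.2). A 5% level, taken from the analysis section of sub-study 1 (4.8), not restated in 7.4, and assumed two-sided.

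**Assumed inputs.** m respondents per community (10 to 30, main case 20); ICC 0.01 to 0.10; equal community sizes; 50% of respondents giving the answer in question; no true location effect. Three layouts: two groups of 6 communities, three countries with 12 communities each, nine districts with 4 each.

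**Formulas.** Design effect DE = 1 + (m − 1) × ICC. With two groups, the actual rejection rate is 2 × [1 − Φ(1.96/√DE)]. With L groups it is P(χ² on L − 1 df > c/DE), where c is the 5% critical value.

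**Main case, m = 20.**
- ICC 0.01: DE = 1 + 19 × 0.01 = 1.19
- ICC 0.05: DE = 1 + 19 × 0.05 = 1.95
- ICC 0.10: DE = 1 + 19 × 0.10 = 2.90

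For example, two groups at ICC 0.05: 2 × [1 − Φ(1.96/√1.95)] = 2 × [1 − Φ(1.404)] = 16.0%.

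| Location groups | Formula, ICC 0.01 / 0.05 / 0.10 | Simulation, same ICCs |
|---|---|---|
| Two (df 1, c = 3.841) | 7.2% / 16.0% / 25.0% | 6% / 15% / 25% |
| Three countries (df 2, c = 5.991) | 8.1% / 21.5% / 35.6% | 8% / 21% / 35% |
| Nine districts (df 8, c = 15.507) | 11.1% / 43.8% / 72.0% | 11% / 44% / 74% |

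The simulation draws beta-binomial answers by community (4,000 replicates per scenario) and applies Pearson's chi-squared test. It agrees with the formula to within about 2 percentage points.

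**Effect of m, ICC fixed at 0.05.** For 10 / 20 / 30 respondents per community, the simulated rates are 11% / 15% / 21% (two groups), 13% / 21% / 31% (three countries) and 22% / 44% / 59% (nine districts).

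**Cases with no inflation.** If location is the community itself, tested as a fixed category with equal true proportions, the simulated rate is 4.8%. For gender balanced within communities, it runs from 5.6% with no correlation down to 2.9% with 30 respondents and ICC 0.20. The same reasoning covers age to the extent that it varies within communities.

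**Does a correction work?** A one-way analysis of variance on community proportions, with its F reference, stayed at 4-6% in every scenario. A first-order Rao-Scott chi-squared with the usual chi-squared reference still rejected at about 8% (two groups of 6) and 10% (nine districts of 4), with m = 20 and ICC 0.05. An F reference brought these to 5% and 9%.

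**The case against.** Four points can be made for the plan.

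1. **The wording is open.** Section 7.4 presents the two methods as examples of standard analyses, and a logistic model with a random effect or robust variance would fit that description. This stands: a reader might infer that the plan commits to tests that ignore community, but the text shows only that no allowance is specified.
2. **Location is undefined.** If it means the communities surveyed, there is no inflation. This also stands, and makes the point conditional. With one community per district, a district contrast is simply a contrast between those communities, and the design could not separate a district effect from a village effect.
3. **The size is assumed.** A reader might infer that false location differences will be declared two to nine times too often. The documents do not support that. For two groups, a twofold excess needs DE of about 1.42 (m = 10 and ICC 0.05 give 1.45), and a ninefold excess needs about 6.73 (m = 30 and ICC 0.20 give 6.80). Neither pair is in the plan. The main case alone spans 6% to 74%, which is 6/5 = 1.2 to 74/5 = 14.8 times nominal.
4. **Little rests on it.** This is the quantitative step of a mixed-methods sub-study with no named outcome, location hypothesis or decision rule. The hypotheses to be validated come from focus groups, and nothing says that they concern districts or countries. The LAMP accuracy analysis (5.7) and the cost-effectiveness model (7.4 item 3) do not use these tests. This limits the importance but does not remove the defect: location is one of three variables that 7.4 names, and the data serve a primary objective.

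**Conclusion.** The point holds in conditional form. Section 7.4 specifies no allowance for community clustering. If location is a unit that contains several sampled communities and answers correlate within communities, the named tests exceed 5%.

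The ranges under working depend on assumed ICC, cluster size and number of communities. They show that the excess can be anything from negligible to severe, and that it grows with the number of locations compared. They do not predict this study's error rate. The consequence is modest and confined to the location comparisons of the questionnaire. The change is still worth making, because it is cheap and the documents contain no other safeguard.

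**What to change.** In section 7.4 item 1:

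- Define location (community, district, country, or rural/urban).
- State that the community identifier is kept with each response.
- For location above community level, test against between-community variation. Suitable methods are a community-level test, a logistic model with a random intercept for community, GEE, or a Rao-Scott chi-squared test.
- Whichever method is used, take an F or t reference based on the number of communities. With few communities per group, the community-level test is the safer choice, since Rao-Scott with an F reference still ran at 9% for nine districts of 4.
- Analyse key stakeholders who belong to no community as a separate group.

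This needs a few sentences, slightly more analysis work and no additional participants. The price is wider intervals and less power for location contrasts.

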## 8 SAFETY CONSIDERATION AND REPORTING

### 8.1 Potential risks

Risks associated with participation in this study are minimal. Swabs are non-invasive and are routinely used programmatically. Finger prick blood samples may cause slight discomfort and bruising; however, these too are routinely used programmatically. Loss of privacy is a potential risk associated with participation in any research project. In this study, it is necessary to confirm cure at four weeks post-treatment, as per WHO guidelines, so it is essential personal details are recorded at the time of recruitment. Potential for loss of confidentiality will be minimized by use of coded study numbers on data collection forms and laboratory samples, and all data will be stored in locked filing cabinets and on encrypted, password-protected computer files. As with the use of any antibiotic, there is a risk that resistance may evolve in either TPE, *H. ducreyi* or in a host's commensal microbiota. There have also been reports of microbial gut community disturbances with azithromycin administration which could have long term implications. However, the data suggest that azithromycin antimicrobial resistance is not long-lived.

#### 8.1.1 Mitigation for COVID-19

COVID-19 transmission is occurring globally. As participation in this study entails interactions with staff from the Ministry of Health and the research team as well as interactions with other members of the community there might be an increased risk of COVID-19 transmission to staff and/or study participants. In order to mitigate these risks we will at all times follow guidance published by WHO on restarting of NTD related activities in the context of COVID-19 (<https://www.who.int/publications/i/item/WHO-2019-nCoV-neglected-tropical-diseases-2020>).

These considerations include but are not limited to:

- 1) We will appoint a COVID-19 focal person in each study site to ensure appropriate SOPS are available and followed, that PPE is available, and liaise with other relevant stakeholders such as Ministries of Health
- 2) We will provide dedicated training to all staff on COVID-19 transmission, infection control and use of PPE.
- 3) Risk-benefit assessments will be carried out for each individual study activity using the framework laid out by WHO. Research activities will only proceed where the benefit is felt to outweigh the risk.
- 4) Before each activity participants and staff will be screened symptoms suggestive of COVID-19 and study staff will use PPE and other appropriate infection prevention and control measures at all times.
- 5) The majority of study activities including screening, enrolment, sample collection and treatment will be conducted outside (as is routine for community NTD screening activities) and will be conducted

using physical distancing. In-depth interviews and focus groups will be conducted using appropriate physical distancing between study staff and participants.

These steps will be reviewed in each country in line with national guidance and any further guidance provided by WHO.

## **8.2 Known potential benefits**

All individuals with a skin ulcer will be referred to relevant health services for treatment with azithromycin, regardless of screening-assay result, as this is an effective treatment for both *T. pallidum* and *H. ducreyi*. Due to the activity of azithromycin against a broad range of bacterial pathogens there is likely to be collateral benefits to taking the prescribed dose of azithromycin for yaws, as has been shown previously. By conducting this study we hope to improve in-country capacity for running field and laboratory studies. If the LAMP tests are shown to be an effective tool each country will have the capacity to use the assay in future studies and eradication campaigns.

## **8.3 Adverse events**

As this is an observational study the likelihood of encountering adverse events is low.

### **8.3.1 Definitions**

- I. Adverse event (AE): Any untoward medical occurrence in a patient or study participant, which occurs between enrolment and follow up (four weeks post enrolment).
- II. Serious adverse event (SAE): Any untoward medical occurrence that:
  - results in death;
  - is life-threatening;
  - requires inpatient hospitalization or prolongation of existing hospitalization;
  - results in persistent or significant disability/incapacity;
  - consists of a congenital anomaly or birth defect.

Serious adverse events are only likely to occur in participants with a severe allergy to penicillin; anyone requiring penicillin treatment will have their history checked. SAEs are rarely associated with azithromycin.

### **8.3.2 Reporting Procedures**

Any questions concerning adverse event reporting will be directed to the Chief Investigator in the first instance. An SAE form will be completed and submitted to the Study Coordination Centre with as much detail as available at that time. If awaiting further details, a follow up SAE report should be submitted promptly upon receipt of any outstanding information.

## **8.4 Follow-up**

No formal study follow-up is planned for participants after the completion of study activities, however, as mentioned in section 5.6, participants will be re-visited four weeks after initial treatment and offered benzathine benzylpenicillin if treatment failure is thought to have occurred.

## **8.5 Data quality assurance and monitoring**

Study staff will be trained on the study protocol prior to the start of study activities at each site. For laboratory testing, this will include centralised and localised training of the TPHD-LAMP technique for laboratory staff working in the local laboratories. Staff at reference laboratories will be trained. Data collection forms will be reviewed by the Study Coordinators and Principal Investigators (PIs) for completeness and accuracy and tested prior to the pilot study. As well as being trained about how to diagnose and assess yaws, field staff and healthcare workers will also be taught about the epidemiology of yaws, treatment options and the importance of good hygiene for combating the disease. All field workers will be trained to perform and interpret serological POCTs, collect lesion swabs and blood spots and other relevant components of the protocol. Refresher training of field and laboratory staff followed by a 2-week pilot period will be conducted before beginning the study at each site, which will allow the investigators and study personnel to identify and resolve potential logistical and technological problems prior to beginning data collection. Standardized protocols and SOPs will be followed for quality control/quality assurance of clinical evaluations, biological sample procurement and preparation, and all laboratory procedures. As well as regular internal audits and monitoring of quality indicators, a central quality management team consisting of the international study coordinator and other team members involved in field coordination, will help to ensure that all laboratory procedures are performed according to SOPs at all sites and with high quality standards. PIs and study coordinators from the different countries will maintain regular contact to ensure consistency in protocol implementation at each site, and will meet regularly with study staff at their site/s to ensure consistency in the collection of data. PIs and study coordinators will participate in regular study group meetings to assess progress of the study, address any difficulties and provide feedback to members of the study group.

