#### **3.1 Overall Study Outline and recruitment**

**Figure 1:** Flow chart of participant recruitment across all three-study countries. Initially we will screen 60,000 people of whom we expect 6000 will present with yaws-like lesions. These 6000 participants, along with 6000 without clinical evidence of yaws will be invited to take part in sub-study 1, the epidemiological analysis. All participants with clinically suspected yaws will be tested with a serology POC test, with positive results being confirmed by second POC test. Those with clinical and serological evidence of yaws will be invited to participate in sub-studies 2 and 3. Additionally, some participants from studies 1-3 along with healthcare workers and key stakeholders will be invited to enrol in study 4.

\* A DPP test is considered positive only if sero-reactive for both treponemal and non-treponemal antibodies.

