## **7 SUB-STUDY 4: A HEALTH ECONOMIC AND SOCIAL SCIENCE EVALUATION OF HEALTHCARE WORKER AND COMMUNITY KNOWLEDGE-ATTITUDES AND PRACTICES IN RELATION TO YAWS AND RELATED DISEASES, AND THEIR DIAGNOSIS.**

### **7.1 Objectives**

- 1) Collect data on community, patient and healthcare worker knowledge, attitudes and practices in relation to yaws and identify specific needs among the community including challenges in accessing prevention, care, and treatment services
- 2) Determine the acceptability and feasibility of TPHD-LAMP assay routine use
- 3) Determine cost-effectiveness of the TPHD-LAMP assay

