## **9 DISSEMINATION OF RESULTS AND PUBLICATION POLICY**

A high degree of public engagement is an integral part of the research plan for this study, and forms the basis of sub-study 4. Stakeholders include research participants, clinicians, policy-makers, and the general public. In the first year of the study meetings will be held with community leaders and with the public at each site to inform local communities about the aims of the study and the methods to be used. Seminars will be organised at participating health facilities to inform medical and nursing staff about the study before it begins.

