## 10 DURATION OF THE STUDY

This study has been funded for 36 months. The duration of participant recruitment is expected to take no more than 12 months. Laboratory testing will coincide with the fieldwork at each site. We anticipate data analysis and dissemination to take one year. The total study is expected to take 36 months.

ACTIVITY	Year 1				Year 2				Year 3			
	1	2	3	4	1	2	3	4	1	2	3	4
Final Version of Study Protocol		Red										
Data and Material Transfer Agreements established			Red									
Appoint of Key Project Staff	Red											
Project Steering Group Meetings	Red	Red	Red	Red	Red	Red	Red	Red	Red	Red	Red	Red
Training needs assessment		Red	Red									
Training			Red	Red								
Monitoring Visits				Red				Red				Red
Production of TPHD LAMP assay for field study	Red	Red	Red	Red								
LAMP SOP development		Red	Red	Red								
Assessment of Reference Labs diagnostic capacity		Red	Red	Red								
Laboratory procurement		Red	Red									
Sub study 1-3 enrolment					Red	Red	Red	Red				
Sample Testing at District and National Laboratories					Red	Red	Red	Red	Red			
Laboratory monitoring					Red	Red	Red	Red	Red			
Sub-study 4 - Patient and Stakeholder Interviews on Diagnostic Testing				Red	Red	Red	Red	Red				
Sub-study 4 - Health-Economic Data Collection and Analysis				Red	Red	Red	Red	Red	Red	Red		
Lab analyses for sub-studies 1-3						Red	Red	Red	Red	Red	Red	

Sub study 1-3 Data Analysis									Red	Red	Red	Red
Community Dissemination Meetings												Red
Final Study Findings Publication												Red

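### The study teaches healthcare workers about yaws and also measures their yaws knowledge, but nothing in the plan separates taught from untaught respondents

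*Combined protocol and SAP*

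**What the plan says.** **What is measured.** Primary objective 5 in section 1.8 is to "Collect data on community, patient and healthcare worker knowledge, attitudes and practices in relation to yaws". Section 7.1 repeats it as the first sub-study 4 objective and adds the purpose of finding community needs and obstacles to care. Under 7.3, focus groups and interviews in each community supply themes for a questionnaire on cause, transmission, diagnosis and care-seeking. The questionnaire then goes to other communities and key stakeholders. Section 7.4 analyses it with chi-squared tests and logistic regression, naming gender, age and location as example variables.

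**What is taught.** Section 8.5, after mentioning training in how to diagnose and assess yaws, says that "field staff and healthcare workers will also be taught about the epidemiology of yaws, treatment options and the importance of good hygiene". That sentence has no date. A separate sentence in 8.5 says "Study staff will be trained on the study protocol prior to the start of study activities at each site".

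**When.** In section 10, the Training row covers year 1 Q3-Q4. The row "Sub-study 4 - Patient and Stakeholder Interviews on Diagnostic Testing" covers year 1 Q4 to year 2 Q4. No row names the KAP work.

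**Other contact with the study.** Section 9: "Seminars will be organised at participating health facilities to inform medical and nursing staff about the study before it begins". In the first year, "meetings will be held with community leaders and with the public at each site to inform local communities about the aims of the study". Section 3.1: "Additionally, some participants from studies 1-3 along with healthcare workers and key stakeholders will be invited to enrol in study 4".

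**The concern.** The subjects taught under 8.5 overlap with the subjects measured under 7.3. If healthcare workers are taught first and questioned afterwards, their answers describe workers who have had the study's training. The objective is meant to describe the state of knowledge that eradication programmes would find, and training given first would tend to hide the gaps it sets out to identify.

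Two further consequences could follow. Focus-group themes are used to build the questionnaire, so a gap already closed by teaching may not become a theme and may then not be asked about. And if training coverage differs between places, a location effect in the 7.4 regressions would mix real differences with differences in training. A pre-training baseline cannot be recovered later, and without a record of exposure the problem cannot be examined in the data.

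**Working it through.** The plan gives no sample size, expected proportion or effect size for the KAP objective, so there is no figure to reproduce. The check compares subject, people, timing and safeguards, then expresses the size as a formula.

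**1. Subject.** 8.5 teaches diagnosis and assessment, epidemiology, treatment and hygiene. The 7.3 questionnaire asks about cause and transmission, diagnosis, and care-seeking. The overlap is direct for diagnosis and for epidemiology against cause and transmission.

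**2. People.** 8.5 teaches healthcare workers as a category. Sections 1.8 and 7.1 measure the same category, and 7.3 names community health workers among the invited groups. The documents do not say that the individuals taught are the individuals sampled. They do not say that they differ either: the 7.2 criteria neither exclude nor identify trained people.

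**3. Timing, from section 10.**
- Training: year 1 Q3 and Q4, 2 quarters.
- Sub-study 4 interviews: year 1 Q4 plus year 2 Q1-Q4, 1 + 4 = 5 quarters.
- Interview quarters before training starts: 0. Overlapping: 1 (year 1 Q4). After training: 4.

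Two limits apply. The interview row is titled for diagnostic testing, so KAP timing is inferred from it as the only sub-study 4 interview row. And because the 8.5 sentence on healthcare workers is undated, its timing is inferred from the Training row.

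**4. Safeguards.** 7.2, 7.3 and 7.4 contain no pre-training measurement, no item on prior study training, no separate reporting of trained respondents, and no exposure variable among those named.

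**5. Size.** Let f be the share of healthcare-worker respondents who were taught, and d the gain in percentage points of correct answers from teaching. The observed proportion correct exceeds the untaught proportion by

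overstatement = f × d.

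Neither input is in the documents. Purely as an assumption, take d from 10 to 30 points and f from 0 to 100%:
- f = 0: 0 × d = 0 points, whatever d is.
- f = 25%, d = 10: 0.25 × 10 = 2.5 points.
- f = 100%, d = 30: 1.00 × 30 = 30 points.

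The assumed range is therefore 0 to 30 points. It shows how the bias scales and does not estimate it. It applies to proportions from the questionnaire. The focus groups and interviews yield themes, for which the effect is only directional.

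**The case against.** The strongest reply is that contamination is not demonstrated. No section says that taught workers are the ones sampled. The 8.5 sentence sits in a data-quality section and is undated. The interview row reads most naturally as the test-acceptability work, which should follow use of the test. The 7.4 regressions use a questionnaire sent to other communities. And a quarterly chart cannot show the order of visits within a site, so a sensible order may already be intended.

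Most of this stands, and it limits the point to a risk. It does not remove the point: the taught and measured categories coincide, no row schedules KAP earlier, and nothing would allow the effect to be detected. Nor are the other communities shown to be untouched by the study, since 7.2 requires community members to live permanently in the selected communities.

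A reader might go further and infer that objective 5 as a whole measures the study's own teaching, counting the section 9 seminars and public meetings and the case search as teaching. The documents do not support this. Section 9 describes seminars and meetings that explain the study, its aims and its methods, not instruction about yaws. Being examined, tested and offered treatment is not teaching. Patients are named in the objective, so drawing some respondents from sub-studies 1-3 is appropriate.

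**Conclusion.** The point holds as a risk to the healthcare-worker part of primary objective 5. The study teaches this group about the subject on which it is measured, the only scheduled interviews coincide with or follow training, and the plan cannot tell taught from untaught respondents. The likely direction is to understate knowledge gaps, assuming that teaching improves answers. The size is f × d, with both terms unknown and zero as a possible value.

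This rests on two inferences: that the Training row includes the teaching of healthcare workers, and that KAP data are collected in the period of the sub-study 4 interview row. For community and patient results the concern is weaker and should be stated only as possible sensitisation. It is worth acting on because the safeguard is cheap and a lost baseline cannot be restored.

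**What to change.** - **7.3:** add one item to the interviews and questionnaire recording whether the respondent has had study training. As a secondary item, record attendance at study meetings or participation in the case search.
- **7.4:** report healthcare-worker results separately for trained and untrained respondents, and include exposure as a covariate in the regressions.
- **Site scheduling:** where it can be arranged, hold healthcare-worker knowledge interviews before that site's training session. The order must be set site by site. Moving the interview row one quarter earlier, to year 1 Q3, would still overlap Training.
- **Keep as planned:** patients from sub-studies 1-3 stay in the main analysis, and LAMP acceptability interviews stay after use of the test. Restricting the main estimate to respondents with no study contact would drop the patients recruited through case search, whom the objective names.

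The cost is one extra question (two with the secondary item), smaller subgroups with less precise estimates, and slightly tighter scheduling at each site. If training status coincides almost completely with location, the covariate will not separate the two, and the report should say so.
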